2.2 Fulvestrant

Fulvestrant is a pure anti-estrogen which is thought to act by downregulating ER expression. In the United States, fulvestrant is approved for the treatment of hormone receptor-positive, metastatic breast cancer in postmenopausal women with disease progression after antiestrogen therapy.²

In two phase III randomized trials conducted in patients with hormone receptor-positive, metastatic breast cancer, who had progressed on either adjuvant or metastatic endocrine therapy, fulvestrant was associated with an objective response rate of 17-19%, not significantly different in comparison to the aromatase inhibitor anastrozole, where the response rate was 15-17%.³ Median time to progression (TTP) was 5.5 months. In the EFECT trial, which enrolled patients who had previously progressed on a nonsteroidal aromatase inhibitor, fulvestrant appeared equally active compared to exemestane, and was associated with a median TTP of 3.7 months, and objective response rate of 7%.⁴ Similar results were observed in the fulvestrant control arm of CALGB 40302, with a median TTP of 4.0 months.⁵

More recently, the CONFIRM trial evaluated a different dose and schedule of fulvestrant, given as a 500 mg IM injection on days 1 and 15 of Cycle 1, followed by 500 mg IM injections on day 1 of each subsequent cycle.⁶ Compared to the 250 mg once monthly schedule, there was a 1 month improvement in median PFS, leading to U.S. FDA approval of the 500 mg dose with loading schedule.

In postmenopausal women with ER-positive tumors, aromatase inhibitors (AI) are now routinely used as part of adjuvant systemic therapy. Based upon data in several phase III trials (conducted prior to the widespread use of aromatase inhibitors in the adjuvant setting), aromatase inhibitors are also widely used in the first-line metastatic setting. After progression on a nonsteroidal AI, a number of strategies are typically used in clinical practice, including a steroidal AI, fulvestrant, estradiol, and tamoxifen (Chia et al, J Clin Oncol 2008; Ellis et al, J Am Med Assoc 2009). There are no prospective trials comparing endocrine strategies in patients after AI failure, and the optimal sequencing of endocrine agents in the metastatic setting is not known. However, the 2010 National Comprehensive Cancer Center guidelines suggest that AIs, fulvestrant, tamoxifen, megestrol acetate, fluoxymesterone, and ethinyl estradiol are all reasonable options as subsequent endocrine therapy after progression on first-line endocrine therapy.

2.3 Study Disease

With over 200,000 new cases per year, breast cancer accounts for nearly one-third of all new cancer diagnoses among women in the United States.⁷ Approximately 40,000 women will die of breast cancer in the U.S. alone.⁷ Worldwide, breast cancer is a major cause of cancer mortality, and was responsible for approximately 458,000 deaths in the year 2008.⁸

There is increasing recognition that breast cancer is comprised of several subtypes, each with distinct features.⁹ The majority of invasive breast cancers express the estrogen receptor (ER) and/or progesterone receptor (PR), and are HER2-negative. Patients with ER and/or PR-positive/HER2-negative (hereafter, designated as ER-positive) tumors tend to have a somewhat

better prognosis than patients with other tumor subtypes. However, in the metastatic setting, median survival is approximately 3 years and long-term remissions are relatively uncommon.

Initial treatment of ER-positive, metastatic breast cancer typically consists of endocrine therapy. Standard endocrine therapy options include tamoxifen, aromatase inhibitors, ovarian suppression, and fulvestrant. The choice of agent(s) varies depending on prior therapy, patient age and menopausal status, and anticipated tolerability. Although endocrine therapies can often be very effective, resistance almost invariably develops. While some patients may be salvaged with further lines of endocrine therapy, virtually all patients eventually progress through the available endocrine agents and require treatment with cytotoxic chemotherapy. For these reasons, in the metastatic setting, strategies to overcome or delay the emergence of endocrine resistance, particularly with treatments that are associated with a favorable toxicity profile in relation to standard cytotoxic agents, would be of great clinical value. Successful strategies could then be evaluated in the adjuvant setting. On average, among women with early-stage, ER-positive/HER2-negative tumors, the relative and absolute benefits of endocrine therapy far exceed that of chemotherapy.¹⁰ Thus, efforts to improve responsiveness to endocrine agents could ultimately have a substantial impact on overall breast cancer outcomes in patients with all stages of breast cancer.

2.4 Rationale for Combining Endocrine Therapy with Ganetespib

Estrogen Receptor expression is typically conserved in metastatic lesions, compared to matched primaries.¹¹ Furthermore, patients who have progressed on a single line of endocrine therapy may subsequently respond to additional lines of endocrine therapy.^{4,12} Thus, ER likely continues to drive a subset of metastatic breast cancers, even after progression. Hormonal therapies for ER-positive breast cancer comprise the earliest and perhaps most efficacious “molecularly targeted” approach to cancer therapy to date. Approaches to augment the efficacy of endocrine therapy and to delay the emergence of resistance have great potential to improve disease outcomes for the most common subtype of breast cancer.

While it is clear that a functional ER contributes to the growth of both hormone-sensitive and refractory tumors, further hormonal manipulation using a range of ligand-dependent therapies only manages to delay tumor progression in the vast majority of cases. Ligand-independent approaches to disrupt ER function may offer greater potential for long-term disease control.

Steroid hormone receptors such as the ER require the molecular chaperone HSP90 to achieve a mature conformation that is capable of high-affinity ligand binding and subsequent activation. These interactions are ATP-dependent, and classical HSP90 inhibitors disrupt formation of mature ER-HSP complexes by blocking ATP binding to the ATP/ADP binding pocket of HSP90. In the presence of the prototypical HSP90 inhibitor geldanamycin (GA), the ER accumulates in an intermediate complex containing a cohort of HSP that target the ER protein for degradation via the ubiquitin-proteasome pathway. As a result, receptor half-life is shortened and cellular levels profoundly decreased.

In addition, Hsp90 inhibitors deplete cellular levels of many signaling proteins, including EGFR, HER2, IGF-1R, VEGF, RAF, and AKT, which have been implicated in the development of

endocrine resistance. A number of efforts to combine endocrine therapy with a molecularly targeted agent have yielded disappointing results. For example, despite promising phase II data, the phase III study of letrozole with or without the mTOR inhibitor CCI-779 was closed early due to lack of efficacy. More recently, CALGB 40302, a randomized trial of fulvestrant with or without the dual EGFR/HER2 inhibitor lapatinib was also closed early due to lack of efficacy.⁵ We hypothesize that this may be the result of selective pressure for escape pathways beyond the specific pathway targeted. The ability of HSP90 inhibitors to simultaneously deplete multiple proteins and destabilize the entire network of signaling pathways that enable endocrine resistance could overcome endocrine resistance and/or delay the emergence of endocrine resistance. Indeed, the first HSP90 inhibitor to be developed clinically, 17-AAG, has already shown promise in patients with HER2-positive breast cancer that have become resistant to trastuzumab.¹³

In preclinical models, 17-AAG markedly disrupts ER transcriptional activity in both tamoxifen-sensitive and tamoxifen-resistant MCF-7 cells.¹⁴ Tumor progression in mice bearing xenografts established using MCF-7 cells that demonstrate tamoxifen dependence for growth in vivo was significantly inhibited by 17-AAG administered on a standard dose and schedule. Further work has demonstrated that geldanamycin, at concentrations with no single agent anti-tumor activity, can virtually eradicate the outgrowth of tamoxifen-resistant MCF-7 cells in culture.

In comparison to 17-AAG, ganetespib is a potent, second-generation, small-molecule HSP90 inhibitor with a chemical structure unrelated to the ansamycin family of first-generation HSP90 inhibitors (e.g. 17-AAG or IPI-504). In preclinical studies, STA-9090 has shown potency up to 100 times greater than the first generation HSP90 inhibitors as well as potency across a wider range of kinases. STA-9090 has activity against a wider range of cancer types. Work by [name] et al (personal communication) has demonstrated more potent anti-proliferative activity against MCF-7 breast cancer cells than 17-AAG (IC₅₀ ~25 nM versus 250-500 nM). Furthermore, it was more effective at limiting the emergence of tamoxifen-resistant clones and in cultures of MCF-7 cells and was synergistic with tamoxifen in a xenograft model.¹⁵ More recently, preliminary evidence of synergistic activity of fulvestrant and STA-9090 has been demonstrated in cell lines, and xenograft studies are underway.

2.5 Summary

This is a randomized phase II trial evaluating fulvestrant with or without ganetespib, a potent, novel HSP90 inhibitor. The primary clinical objective is progression-free survival. We hypothesize that ganetespib will augment the efficacy of fulvestrant and be associated with an improvement in progression-free survival.

Secondary clinical endpoints include objective response rate (among patients with measurable disease at baseline), safety/tolerability, clinical benefit rate (CR + PR + SD \geq 6 months), and overall survival.

The correlative objectives of this study include evaluation of the relationship between HSF1 and clinical outcome, alterations in heat-shock network function, ER expression and transcriptional activity, and alterations in other relevant downstream targets. Patients who enroll on this trial will also be approached regarding an ¹⁸FES-PET companion study (which will be written as an entirely separate, IRB-approved protocol) when it is available.

CONFIDENTIAL

This document is confidential. Do not disclose or use except as authorized.

3. PARTICIPANT SELECTION

Laboratory tests required for eligibility must be completed within 14 days prior to randomization. Baseline measurements must be documented from tests within 28 days prior to randomization. QTc must be documented by 12-lead ECG within 28 days prior to randomization. Other non-laboratory tests must be performed with the timeframe specified.

3.1 Eligibility Criteria

Participants must meet the following criteria on screening examination to be eligible to participate in the study:

- 3.1.1 Participants must have histologically confirmed invasive breast cancer that is metastatic or unresectable locally advanced. Histological documentation of metastatic/recurrent breast cancer is not required if there is unequivocal evidence for recurrence of the breast cancer.
- 3.1.2 Estrogen and/or progesterone receptor positive breast cancer, as determined by pathology from either primary or metastatic site(s). Central confirmation is not required.
- 3.1.3 HER2 negative, defined as 0-1+ by immunohistochemistry or FISH-negative (ratio < 2.2). Central confirmation is not required.
- 3.1.4 Postmenopausal women are eligible. Postmenopausal is defined as any of the following:
- Age > 60 years
 - Age > 45 with intact uterus and amenorrhea for 12 months or more
 - Follicle stimulating hormone (FSH) levels within postmenopausal range according the ranges established by the testing facility
 - Premenopausal women who have been on a GnRH agonist for at least 3 consecutive months prior to study entry are eligible. Women in this group **MUST** remain on the GnRH agonist for the duration of protocol treatment.
 - Status-post bilateral oophorectomy-After adequate healing post surgery.
- 3.1.5 Women and men, age \geq 18 years of age
- 3.1.6 Measurable disease is required. Measurable disease is defined as at least one lesion that can be accurately measured in at least one dimension (longest diameter to be recorded) as \geq 20 mm with conventional techniques or as \geq 10 mm with spiral CT scan. Bone lesions, leptomeningeal disease, ascites, pleural/pericardial effusions, lymphangitis cutis/pulmonis, inflammatory breast disease, abdominal masses identified by physical exam that are not measurable by reproducible imaging techniques, and cystic lesions are all considered non-measurable. See section 10 for details. **As of 4/30/14, the evaluable/non-measurable cohort has been filled and only patients with measurable disease are allowed moving forward. Prior to 4/30/14, up to 20% of patients entered on this trial (i.e. 14 patients) were entered with evaluable but nonmeasurable disease.**

CONFIDENTIAL

This document is confidential. Do not disclose or use except as authorized.

3.1.7 Endocrine resistant breast cancer, defined as either:

- Relapsed while on adjuvant endocrine therapy or within 1 year of completion of adjuvant endocrine therapy

-OR-

- Progression through at least one line of endocrine therapy for metastatic or locally advanced breast cancer. There is no limit on the number of prior endocrine therapies received.

3.1.8 Patients may have received up to one prior line of chemotherapy for metastatic or unresectable locally advanced breast cancer.

3.1.9 Patients may have initiated bisphosphonate therapy prior to start of protocol therapy. Bisphosphonate therapy may continue during protocol treatment. Such patients will have bone lesions considered evaluable for progression.

3.1.10 Patients must be at least 2 weeks from prior chemotherapy or radiotherapy, or any investigational drug product, with adequate recovery of toxicity to baseline, or grade ≤ 1 , with the exception of alopecia and hot flashes. There is no washout period for prior endocrine therapy.

3.1.11 ECOG Performance Status 0-1 (Appendix A)

3.1.12 Availability of a tissue block from initial breast cancer diagnosis and/or metastatic recurrence. If a tissue block is not available, 10-20 unstained slides may be provided as an alternative. If unstained slides will be provided, they should not be sent until specifically requested by the DFCI study coordinator.

3.1.13 For patients with biopsy-accessible disease, patients must be willing to undergo a required on-treatment research biopsy. This biopsy will occur on ~Cycle 2 Day 9.

3.1.14 Biopsies may be done with local anesthesia or intravenous conscious sedation, according to standard institutional guidelines.

3.1.15 Research biopsies requiring general anesthesia are not allowed on this protocol unless a biopsy is being obtained simultaneously for clinical reasons, in the judgment of the patients' treating physician.

3.1.16 Patients who undergo an attempted on-treatment research biopsy and in whom inadequate tissue is obtained are still eligible to continue protocol therapy. They will not be required to undergo a repeat biopsy attempt.

CONFIDENTIAL

This document is confidential. Do not disclose or use except as authorized.

3.1.17 Participants must have normal organ and marrow function as defined below:

- Absolute neutrophil count $\geq 1,500/\text{mcL}$
- Platelets $\geq 100,000/\text{mcL}$
- Hgb $\geq 9 \text{ mg/dL}$ (which may be post transfusion)
- Total bilirubin $< 1.5 \text{ X}$ institutional upper limit of normal (patients with documented Gilbert's disease are allowed total bilirubin up to 3X ULN)
- AST (SGOT)/ALT (SGPT) $\leq 2.5 \text{ X}$ institutional upper limit of if no liver metastases; and $< 5 \text{ X}$ institutional upper limit if liver metastases are present
- Creatinine $\leq 2\text{X}$ institutional upper limit of normal

3.1.18 Adequate IV access

3.1.19 Fulvestrant is contraindicated in pregnancy (category D). The effects of ganetespib on the developing human fetus are unknown. For these reasons, women of child-bearing potential and men must agree to use adequate contraception (hormonal or barrier method of birth control; abstinence) prior to study entry and for the duration of study participation. Should a woman become pregnant or suspect she is pregnant while participating in this study, she should inform her treating physician immediately. Premenopausal women who have been on a GnRH agonist for at least 3 consecutive months prior to study entry are eligible. Women in this group **MUST** remain on the GnRH agonist for the duration of protocol treatment. Such patients should be counseled that GnRH agonists alone may not be adequate contraception and that adequate contraception (hormonal or barrier method of birth control; abstinence) prior to study entry and for the duration of study participation should be employed.

3.1.20 Ability to understand and the willingness to sign a written informed consent document.

3.1.21 Patients on therapeutic dose anti-coagulation with warfarin, LMWH, or other anti-coagulants will be allowed to participate in the study. However, the anti-coagulants should be held pre- and post- research biopsy (when applicable) as per institutional standards. The risks of a temporary hold of anti-coagulation should be carefully considered and explained to the patient as part of the informed consent process. If it is not felt to be in the best interest of the patient to have anti-coagulation held, the patient may still enter the study, but should not undergo a research biopsy.

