5. TREATMENT PLAN

Treatment must begin within 7 days of randomization. Treatment will be administered on an outpatient basis. Expected toxicities and potential risks as well as dose modifications for fulvestrant and ganetespib are described in Section 6 (Expected Toxicities and Dosing Delays/Dose Modification). No investigational or commercial agents or therapies other than those described below may be administered with the intent to treat the participant's malignancy.

Patients who enter the study and who are postmenopausal on the basis of GnRH agonist treatment must continue that treatment throughout the duration of the study.

A total of 71 patients will be enrolled in the study. Patients will be stratified according to whether or not they have measurable disease (by RECIST 1.1) at baseline and then randomized 1:2 to the two treatment arms:

Arm A: Fulvestrant (n=24)

Arm B: Fulvestrant plus Ganetespib (n=47)

Patients who are randomized to Arm A may cross over to Arm C (Fulvestrant plus ganetespib) at the time of centrally confirmed progression.

In both Arms A and B, each cycle will be ~28 days in length. Treatment will continue until disease progression (possibly the second progression on the combination therapy, if the patient was originally randomized to Arm A fulvestrant), unacceptable toxicity, withdrawal of consent, or death, whichever comes first. Follow up (specifically, tumor measurements as scheduled in

CONFIDENTIAL

This document is confidential. Do not disclose or use except as authorized.

the protocol) will continue until disease progression, withdrawal of consent, death, or the start of other anti-neoplastic therapy, whichever comes first.

Minor schedule changes owing to observed holidays, inclement weather, etc. are permitted. Patients may interrupt therapy for protocol-directed reasons (i.e. toxicity). From Cycle 3 forward, patients may also interrupt therapy for personal preferences (e.g., holidays, vacations). Treatment should resume according to protocol guidelines. Patients may not voluntarily omit fulvestrant at any time. From Cycle 3 forward, patients may not voluntarily omit more than 2 doses of ganetespib in a single cycle, except as detailed below. See Section 9.0 Study Calendar for additional details.

It is anticipated that some patients in Arm B or Arm C may either choose or be taken off of ganetespib for reasons other than disease progression (i.e., for toxicity or patient preference). The following guidelines apply:

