9.1 STUDY CALENDAR A

ARM A: Fulvestrant Alone—Initial Therapy

Note: The study calendar below describes initial study procedures for Arm A.

- Patients who progress on fulvestrant alone may cross over to Arm C, fulvestrant + ganetespi and should be followed at that time according to Study Calendar C, or they may elect to discontinue study treatment altogether.
- Patients who discontinue fulvestrant for a reason other than progression should be followed at that time according to Study Calendar D.
- *Patients who are taken off Arm A for reason other than progression and who are not followed on study calendar D for any reason, should have “off-treatment” evaluation and tests as described in the “At time of progression or off-treatment” column below. Patients are then followed for survival status as described in the “follow-up” column below.

	Pre-Study	C1 D1	C1 D15	C2 D1	C2 D8	C2 D9	C3 D1	Day 1 of each cycle	Every 2 cycles	At time of progression or off-treatment*	Follow-Up
Informed consent	X										
Confirm eligibility	X										
Demographics	X										
Medical History	X										
Concurrent medications	X	X	X	X			X	X		X	
Physical examination		X	X	X			X	X		X	
Vital signs ^a		X	X	X			X	X		X	
Height		X									
Weight		X								X	
ECOG performance status	X	X	X	X			X	X		X	
CBC w/diff, plts	X	X		X			X	X		X	
Serum chemistry ^b	X	X		X			X	X		X	
PT,PTT ^c											
B-HCG ^d	X										
CEA, CA27-29 ^e		X					X ^c		X ^c	X	
12-lead EKG	X									X ^f	
Adverse event evaluation ^g	X	X	X	X			X	X		X	
Tumor measurements ^h	X								X ^h	X	
Bone scan ⁱ	X								X ⁱ	X	
Fulvestrant		X	X	X			X	X			
Research specimen collection (see section 9.5)	X	X			X	X				X	
Survival Status (see Section 5.1.16)											X q3months

CONFIDENTIAL

This document is confidential. Do not disclose or use except as authorized.

- a. Vital signs: heart rate, blood pressure, respiratory rate
- b. Serum chemistry: sodium, potassium, chloride, bicarbonate, blood urea nitrogen, creatinine, glucose (random), total bilirubin, alkaline phosphatase, ALT, AST, albumin, calcium, magnesium, phosphorus
- c. PT, PTT if clinically indicated prior to biopsy (-ies) per standard institutional guidelines.
- d. In women of childbearing potential only (including premenopausal women with intact uterus and ovaries on GnRH agonist).

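### Section 3.1.19 accepts hormonal contraception for women with ER and/or PR positive cancer, including those eligible only through mandatory GnRH agonist suppression, which is inconsistent with the required endocrine background

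*Combined protocol and SAP*

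**What the plan says.** Section 3.1.19 asks women of child-bearing potential, and men, to "use adequate contraception (hormonal or barrier method of birth control; abstinence) prior to study entry and for the duration of study participation". It then turns to premenopausal women on a GnRH agonist, who must remain on it during protocol treatment. They are to be counselled that "GnRH agonists alone may not be adequate contraception and that adequate contraception (hormonal or barrier method of birth control; abstinence") should be used, again from before entry and throughout participation.

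The entry route for these women is in Section 3.1.4: "Premenopausal women who have been on a GnRH agonist for at least 3 consecutive months prior to study entry are eligible". Section 5 describes them as "postmenopausal on the basis of GnRH agonist treatment must continue that treatment throughout the duration of the study". Note d to Study Calendars A and B requires the pregnancy test "In women of childbearing potential only (including premenopausal women with intact uterus and ovaries on GnRH agonist"), so the protocol itself counts them as of childbearing potential. Section 3.1.2 requires ER and/or PR positive disease in every participant.

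**The concern.** The protocol admits this group on condition that ovarian function stays suppressed, and then tells investigators that a hormonal contraceptive is an acceptable addition. The two instructions pull in opposite directions. One fixes the endocrine background on which fulvestrant is given; the other leaves part of that background to the choice of the woman and her physician.

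At stake are patient safety and a consistent background endocrine treatment in a trial of an endocrine regimen. The permission runs for the whole of study participation, so it bears on women already enrolled as well as on new entrants.

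**Working it through.** No calculation applies, because the point depends on no sample size, event count or error rate. The check sets 3.1.19 beside the protocol's own premises, and then beside every rule that might override it.

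**Counts, by reading**
- The parenthesis listing hormonal methods, barrier methods and abstinence occurs 2 times, both in 3.1.19. The first mention covers women and men; the second is written only for the GnRH agonist group.
- Hormonal contraception is 1 of the 3 listed options.
- The GnRH agonist is 1 of 5 routes in 3.1.4. The other four are age over 60, age over 45 with 12 months' amenorrhea, FSH in the postmenopausal range, and bilateral oophorectomy. Among women, the contraception clause therefore applies chiefly to the GnRH agonist group.

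**Premises in the protocol**
- Section 2.2 gives the setting of fulvestrant's approval: "fulvestrant is approved for the treatment of hormone receptor-positive, metastatic breast cancer in postmenopausal women with disease progression after antiestrogen therapy".
- Section 2.3 treats suppression of the ovaries as treatment: "Standard endocrine therapy options include tamoxifen, aromatase inhibitors, ovarian suppression, and fulvestrant".
- Section 2.4 states that "it is clear that a functional ER contributes to the growth of both hormone-sensitive and refractory tumors".
- Section 2.2 also names estradiol among the strategies used after a nonsteroidal aromatase inhibitor, and reports guidelines that list megestrol acetate and ethinyl estradiol as reasonable later endocrine options. The protocol thus regards exogenous hormones of these kinds as active in the disease.

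Together these imply that the hormonal background should be controlled. They do not say in which direction a contraceptive would act.

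**Rules that might override the permission**
- Exclusion 3.2.4 mentions endocrine therapy, but only among agents given with intent to treat the malignancy. A contraceptive is not given for that purpose.
- Section 5 carries the same intent limit.
- Section 5.4 bars other antineoplastic agents, with exceptions for bisphosphonates and GnRH agonists. It has no intent limit, but it does not mention contraceptives, whereas 3.1.19 names them as acceptable.
- The CYP3A4 and CYP2C19 paragraph in 5.4 is described there as precautionary only, and contraceptives are not among its examples.
- Appendix I, the list of drugs linked to torsades de pointes, contains no contraceptive.
- Section 5.4 also requires medications to be noted in the medical record. That would show the use without preventing it.

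At best, a site would have to infer a bar from general wording in 5.4 against a specific permission in 3.1.19.

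**The case against.** The strongest reply is that none of the premises speaks to contraceptive hormones. The approval statement describes an indication the trial already goes beyond, since it enrols men and GnRH-suppressed women. Ovarian suppression is one option in a list. The paragraph in Section 2.4 on ER function goes on to favour ligand-independent approaches. Section 2.2 names estrogens and a progestin as treatments, so the documents nowhere say that exogenous hormone is contrary to therapy. This stands as far as harm is concerned: the documents do not show it. It does not remove the inconsistency. If these hormones act on the disease, they should not be an optional, uncontrolled exposure beside mandatory suppression.

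A second reply is that 5.4 may already catch some products, because ethinyl estradiol and megestrol acetate appear in Section 2.2 as anticancer options. That is fair, and it makes 5.4 ambiguous; but the specific text in 3.1.19 points the other way. The consent form and eligibility checklist were not available, so wording at site level could not be checked.

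A third reply is that the first mention also serves male participants, so only the second is directed solely at the group in question. That is correct, and the second mention is enough for the point.

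A fourth is that fulvestrant is contraindicated in pregnancy and ganetespib may be teratogenic (3.1.19 and 3.2.11), so removing a contraceptive option has a cost. It does, and the change has to deal with it.

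A reader might go further and infer that the clause harms patients, distorts the PFS comparison, or makes hormonal contraception compulsory. The documents support none of these. They contain no data on contraceptive hormones in this disease; the rule is the same in both randomized arms; and the method is an option.

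**Conclusion.** The point holds as an inconsistency between a written permission and the endocrine background the protocol requires. It is not a literal contradiction, since a woman can comply with both rules at once.

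Its size cannot be stated. The documents give neither the number of women on a GnRH agonist nor how many would choose a hormonal method, and they do not divide hormonal methods into estrogen-containing, progestin-only or local ones. No size of harm, frequency, bias or effect on power is claimed. Severity is low to moderate.

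The conclusion rests on two readings: that the specific wording of 3.1.19 prevails over the general bar in 5.4, and that naming these hormones as endocrine options in Section 2.2 is reason enough to control exposure to them.

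**What to change.** - In 3.1.19, in both the general sentence and the GnRH agonist sentence, require female participants to use effective non-hormonal contraception: a barrier method, another effective non-hormonal method, or abstinence. Leave partners of male participants unrestricted.
- In 5.4, add a line stating that hormonal contraceptives are not permitted for female participants. Do not limit it to systemic products; otherwise a local hormonal method would be barred in one section and not in the other.
- Extend the counselling already required in 3.1.19 to cover effective non-hormonal methods.
- If the consent form or eligibility checklist repeats the present wording, bring it into line.

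The editing cost is a few words in two sentences, one new line and any matching text; no statistical figure changes. The real cost is that female participants lose one of three listed options where pregnancy carries fetal risk. Barrier methods and abstinence remain, and the added counselling is there to offset the loss, though the documents hold no data on how fully it would.
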